4.0 SELECTION AND WITHDRAWAL OF SUBJECTS

4.1 Study Population

The target population will consist of treatment-naïve and treatment experienced male and female subjects (18-70 years of age, inclusive) with CHC infection. Up to 320 subjects will be enrolled into up to 16 treatment arms.

4.2 Inclusion Criteria

Main Inclusion Criteria for All Subjects:

1. Subject has provided written consent.
2. In the Investigator's opinion, the subject is able to understand and comply with protocol requirements, instructions, and protocol-stated restrictions and is likely to complete the study as planned.
3. Male or female, 18–70 years of age.
4. Body mass index (BMI) 18–35 kg/m², inclusive.
5. A woman of childbearing potential must have a negative serum (β -human chorionic gonadotropin) pregnancy test at screening.
6. Female subjects must either:
 - not be of childbearing potential defined as:
 - i. Postmenopausal for at least 12 months (i.e., 2 years of amenorrhea without an alternative medical cause) and a serum follicle stimulating hormone (FSH) level in the postmenopausal range (per reference laboratory), OR
 - ii. Surgically sterile (e.g., underwent total hysterectomy, bilateral oophorectomy, or bilateral tubal ligation/bilateral tubal clips without reversal operation), or otherwise incapable of becoming pregnant,
 - OR

-
- i. be of childbearing potential AND
 - ii. not heterosexually active (e.g., abstinent or homosexual) from screening until 6 months after study drug administration (or longer, if dictated by local regulations), OR
 - iii. if heterosexually active
 - o have a vasectomized partner (confirmed sterile per verbal account of the subject), OR
 - o using an acceptable method of birth control from screening and agree to continue to use the same method of contraception throughout the study and for 6 months after study drug administration (or longer, if dictated by local regulations). Acceptable methods of birth control include: oral hormone-based contraceptives, an IUD, being either hormonal (i.e., IUS) or non-hormonal, other non-oral hormone-based contraception methods (e.g., injectable, implants, transdermal system, vaginal ring), or a double-barrier method (eg, male condom + either a diaphragm or cervical cap with or without spermicide). Condom use by male partners with reproductive potential is required in all circumstances except when female subjects are using acceptable birth control methods which are long term in nature and do not require high degrees of compliance (e.g. IUDs, depot-form injectables, implants).
 - o See also the NOTES regarding contraception considerations that apply to men and women at the bottom of Inclusion #7
7. Male subjects must either:
- be surgically sterile (had a vasectomy), or otherwise incapable of fathering a child, OR
 - not be heterosexually active (e.g., abstinent or homosexual) from enrollment (Day 1) in the study until at least 6 months after study drug administration, OR
 - if heterosexually active:
 - o have a partner who is postmenopausal (2 years amenorrhea), surgically sterile (e.g., has had a total hysterectomy, bilateral oophorectomy, or bilateral tubal ligation/bilateral tubal clips without reversal operation), or otherwise incapable of becoming pregnant OR
 - o be practicing an acceptable method of birth control from enrollment in the study (Day 1) and agree to continue to use the same method of contraception throughout the study and for at least 6 months after study drug administration (or longer, if dictated by local regulations). An acceptable method of birth

control for male subjects is a double-barrier method (e.g., male condom+either diaphragm or cervical cap with or without spermicide).

NOTE 1: Male subjects with a female partner who uses hormonal contraceptives (oral, injectable, implants) or a hormonal (IUS) or non-hormonal IUD and male subjects who are vasectomized or otherwise incapable of fathering a child are not required to use additional contraceptive methods.

NOTE 2: Sexual abstinence is considered a highly effective method **only** if defined as refraining from heterosexual intercourse during the entire period of risk associated with the study drug. The reliability of sexual abstinence needs to be evaluated in relation to the duration of the study and the preferred and usual lifestyle of the subject.

NOTE 3: A male and female condom should not be used together due to risk of breakage or damage caused by latex friction.

NOTE 4: Contraceptive use by men and women should be consistent with local regulations regarding the use of contraceptive methods for subjects participating in clinical studies if these are stricter than what is proposed in these inclusion criteria.

8. Subjects must agree to refrain from sperm/egg donation from start of dosing through 6 months after the completion of study drug administration.
9. GT1a or 1b or GT2 or 3 CHC, depending on cohort, with positive HCV antibody and a positive HCV RNA at screening including documentation of CHC infection for at least 6 months. Genotype testing must occur at a screening visit. NOTE: GT1 patients are eligible for inclusion even if they cannot be successfully subtyped unless a specific subtype is required for a cohort.
10. Screening HCV RNA viral load $\geq 50,000$ IU/mL, except for subjects with compensated cirrhosis (Child-Pugh Class A) who may have HCV RNA viral load $\geq 10^4$ IU/mL.
11. Treatment naïve (i.e., no prior exposure to any approved or investigational drug(s) including direct-acting antivirals, and interferon-based treatment regimens) or, in subjects with cirrhosis, treatment experienced (defined as subjects who experienced virologic relapse after receiving a full course of pegylated interferon+ribavirin (peg/riba) treatment). Prior use of any direct acting antiviral in combination with peg/riba is not permitted.
12. Fibroscan, collected within 6 months of baseline visit, with liver stiffness score ≤ 12.5 kPa to be eligible (except for subjects with cirrhosis, see below).
 - Subjects with compensated cirrhosis must meet the Child-Pugh Class A definition (see [Appendix G](#)) and at least one of the following criteria:

- iii. Liver biopsy result indicating the presence of cirrhosis (e.g., Metavir F4; Ishak >5) or
 - iv. Fibroscan evaluation with a liver stiffness score >12.5 kPa
13. Subject is otherwise in good health as deemed by the investigator, based on the findings of a medical evaluation including medical history, physical examination, laboratory tests and ECG.
 14. Willing to avoid prolonged sun exposure and use of tanning devices while taking SMV and through 4 weeks of follow up. Subjects should also be advised to use a broad-spectrum sunscreen and lip balm of at least sun protection factor >30 to help protect against potential sunburn.

4.3 Exclusion Criteria

Subjects will be ineligible for this study if they meet **any** of the following criteria:

1. Pregnant, planning on becoming pregnant (during treatment and up to 6 months after the EOT), or breast-feeding female subject, or male subject whose female partner is pregnant or planning on becoming pregnant (during treatment and up to 6 months after the EOT)
2. Other than CHC with or without compensated cirrhosis, clinically significant cardiovascular, respiratory, renal, gastrointestinal, hematologic, neurologic, thyroid or any other medical illness or psychiatric disorder, as determined by the Investigator and/or Sponsor's Medical Monitor.
3. History or other clinical evidence of significant or unstable cardiac disease (e.g., angina, congestive heart failure, myocardial infarction, diastolic dysfunction, significant arrhythmia, coronary heart disease, and/or clinically significant ECG abnormalities), moderate to severe valvular disease or uncontrolled hypertension at screening.
4. Screening echocardiogram ejection fraction <55% or any other echocardiographic finding suggestive of clinically relevant cardiomyopathy.
5. Creatinine clearance of <60 mL/min (Cockcroft-Gault).
6. Positive test for HAV IgM, HBsAg, or HIV Ab.
7. Abnormal screening laboratory results that are considered clinically significant by the investigator.
8. History of clinical hepatic decompensation, e.g., variceal bleeding, spontaneous bacterial peritonitis, ascites, hepatic encephalopathy or active jaundice within the last year.
9. Any condition that, in the opinion of the investigator, would compromise the study's objectives or the well-being of the subject or prevent the subject from meeting the study requirements.

10. Participation in an investigational drug trial or having received an investigational vaccine within 30 days or 5 half-lives (whichever is longer) prior to study medication.
11. Clinically significant abnormal screening ECG findings (e.g., PR >200 msec, QRS interval >120 msec or corrected QT interval (QTc) >450 msec for male subjects and >470 msec for female subjects), based on an average of triplicate ECGs. Any evidence of heart block or bundle branch block is also exclusionary.
12. History or family history of abnormal ECG intervals, for example prolonged QT syndrome (*torsade de pointes*) or sudden cardiac death.
13. The subject has a positive prestudy drug screen, including methadone unless the drug is prescribed by the subject's physician. The list of drugs that should be screened for includes amphetamines, barbiturates, cocaine, opiates, phencyclidine (PCP), and benzodiazepines. Drug use without a physician prescription may be permitted on a case by case basis after review by the Sponsor in consultation with the investigator.
14. Laboratory abnormalities including:
 - Hematocrit <0.34
 - White blood cell counts <3,500/mm³ (<1,000/mm³ for subjects with compensated cirrhosis)
 - Absolute neutrophil count <1,000/mm³ (<750/mm³ for subjects with compensated cirrhosis)
 - Platelets ≤120,000/mm³ (platelets <70,000/mm³ for subjects with compensated cirrhosis)
 - Glycosylated hemoglobin (HbA1C) >55 mmol/mol or 7.2%
 - Prothrombin time ≥1.5 × ULN
 - Albumin ≤32 g/L, bilirubin ≥1.5 mg/dL at screening (subjects with documented Gilbert's disease allowed)
 - Serum ALT concentration ≥5 × ULN
 - CK >1.5 × ULN

A single repeat laboratory evaluation under appropriate conditions (e.g., fasted, no antecedent exercise) is allowed for eligibility determination.

15. Any condition possibly affecting drug absorption (e.g., gastrectomy or other significant gastrointestinal tract surgery, such as gastroenterostomy, small bowel resection, or active enterostomy).
16. Clinically significant blood loss or elective blood donation of significant volume (i.e., >500 mL) within 60 days of first dose of study drug; >1 unit of plasma within 7 days of first dose of study drug.

17. Evidence of clinically relevant active infection that would interfere with study conduct or its interpretation.
18. History of regular alcohol intake >10 standard drinks per week of alcohol for females and >15 standard drinks per week for males (one unit is defined as 10 g alcohol) within 3 months of the screening visit.
19. The use of prohibited medications, including prescription, over-the-counter (OTC) medications, herbal medications, inducers or inhibitors of CYP450 enzymes or drug transporters (including P-gp) within 14 days prior to the first dose of study medication is excluded, unless previously approved by the Sponsor's Medical Monitor. NOTE: Chronic medication use is permitted so long as they are medically necessary, deemed acceptable by the Principal Investigator and Medical Monitor, and not Prohibited Medications (see Section 5.12).
20. Hypersensitivity to the active substances (including sulfa allergy) or to any of the excipients of AL-335, ODV or SMV.
21. Evidence on recent (within 6 months) liver ultrasound of hepatic mass or lesion concerning for malignancy (subjects with cirrhosis only).

4.4 Subject Screening and Enrollment

Screening procedures will occur when a subject signs and dates an Institutional Review Board (IRB)/Independent Ethics Committee (IEC)/Ethics Committee (EC) approved informed consent form (ICF) and provides authorization to use protected health information. The ICF will be completed prior to any study-specific procedures. The use of a site-specific generic consent form, approved by the local EC, may be used prior to approval of the study specific consent form at the Sponsor's discretion.

To enroll, the investigator will verify eligibility according to all inclusion and exclusion criteria (Sections 4.2 and 4.3). Any questions regarding eligibility should be addressed to the Sponsor's Medical Monitor prior to enrollment.

4.4.1 Screening Examination

A screening examination should be performed between -50 and -1 days before the start of the study. Subjects must fulfill all entry criteria to be accepted into the study.

A screen failure log must be maintained by the investigator.

At the screening examination, the procedures outlined in Table 6-1 through Table 6-3 will be performed to establish each candidate's general health and qualifications for enrollment into the study.

For re-screened subjects who were previously screened in the study and found to be eligible but were not enrolled due to limited cohort slot enrollment availability or other nonmedical reasons or were ineligible under a prior protocol version but became eligible under an approved later

version of the protocol, the screening procedures outlined in Table 6-1 through Table 6-3 should be repeated with the exclusion of the following:

- Echocardiogram (as long as the most recent study echocardiogram was obtained within the past 4 months)
- HCV genotype
- Hepatitis and HIV screen
- IL28B genotype

4.5 Subject Completion

A subject will be considered to have completed the study if he or she has completed the assessments at the Week 24 follow-up visit.

4.6 Subject Discontinuation

The primary consideration in any determination to discontinue a subject's participation must be the health and welfare of the subject. Reasons for discontinuation may include, but are not limited, to the following:

- An AE or SAE, drug reaction, or complication, whether related or not to study drug, which precludes continuation of treatment with study drug. This includes the development of allergic reactions or other potentially serious drug reactions to the study medication.
- Noncompliance with study drug dosing.
- Noncompliance with study procedures.
- Lost to follow up.
- Subject's right to withdraw consent at any time during the study, with or without a stated reason.
- The principal investigator's opinion that it is not in the subject's best interest to continue study participation.
- Sponsor's decision to terminate the study (e.g., see section 4.7).

Subjects are free to discontinue their participation at any time during this clinical trial. The investigator has the right to remove any subject from treatment with study drug or participation in the study. However, Alios requests that the investigator consult with the Sponsor's Medical Monitor before prematurely removing a subject. For subjects that discontinue study drug prematurely, sites are strongly encouraged to follow these subjects as prescribed in this protocol as much as possible as this is the primary mechanism to ensure subject safety.

Any subject who decides to discontinue participation in the study, or meets the discontinuation criteria specified below, should undergo early discontinuation procedures (Section 4.6.2).

4.6.1 Subject Treatment Discontinuation Criteria

If a subject's study drug treatment must be discontinued before the end of the treatment regimen, this will not result in automatic withdrawal of the subject from the study.

A subject's study drug treatment (AL-335, SMV and ODV) must be permanently discontinued if:

- The investigator believes that for safety reasons (e.g., AE), it is in the best interest of the subject to discontinue study drug treatment.
- The subject becomes pregnant.
- The subject has evidence of muscle injury (Section 7.5.1) or cardiac toxicity (Section 7.5.2 and 7.5.3).
- The subject has a Grade 4 rash; see Section 7.6.
- The subject has a Grade 3 or 4 allergic reaction; see Section 7.7.
- The subject has a confirmed Grade 4 ALT and/or AST value that is $>2\times$ the baseline value; see Section 7.9.
- The subject has a confirmed Grade 4 bilirubin value which is considered a sign of worsening liver disease, or for which there is no identifiable explanation; see Sections 7.8 and 7.9.
- The subject has severe worsening of hepatic disease.
- The subject has a confirmed diagnosis of pancreatitis.
- The subject has a Grade 4 AE or laboratory abnormality at least possibly related to 1 of the study drugs and which is considered clinically significant (laboratory abnormalities only).
- The subject requires treatment with any of the medications reported on the list of disallowed medications; see Section 5.12.
- The subject experiences inadequate virologic response or viral breakthrough (refer to Definitions)
- An event occurs which triggers the study treatment stopping criteria (Section 4.7.1)

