7.5.2 Cardiotoxicity

A theoretical risk of nucleosides is mitochondrial toxicity that can manifest as cardiac toxicity/congestive heart failure. Surveillance for this theoretical risk will be done in this study via assessments of AEs, ECGs and echocardiograms, which will be obtained at specified timepoints during the treatment period in this study.

In order to effectively monitor for potential treatment-related cardiotoxicity during the study, subjects presenting at screening must have:

- ECG PR interval must be < 200 msec and there must be no evidence of any conduction blocks.
- echocardiogram ejection fraction (EF) must be $\geq 55\%$.

During the treatment period, emergence of or changes in symptoms or clinically significant findings in ECG may trigger the following stopping criteria:

If a first degree AV block is diagnosed and:

- The PR interval is > 200 msec but ≤ 240 msec, study drugs can be continued. Close monitoring with weekly ECG is recommended.
- The PR interval is > 240 msec but ≤ 300 msec (confirmed by a repeat triplicate analysis at least 30 minutes after the initial assessment), an assessment of the subject's clinical status, including symptoms, physical examination and other clinical parameters should be made. Based on this assessment, the study drugs may or may not be continued. Close monitoring with weekly ECG is recommended.

- The PR interval is >300 msec (confirmed by a repeat triplicate analysis at least 30 minutes after the initial assessment, irrespective of presence or absence of clinical symptoms), ODV must be discontinued. The Investigator and Sponsor Medical Monitor must determine whether or not continued dosing with AL-335 and SMV is acceptable for subjects that discontinue ODV.
- If a second degree or higher AV block is diagnosed (confirmed by a repeat triplicate analysis at least 30 minutes after the initial assessment and irrespective of presence or absence of clinical symptoms), ODV must be discontinued. The Investigator and Sponsor Medical Monitor must determine whether or not continued dosing with AL-335 and SMV is acceptable for subjects that discontinue ODV.

All study medications must be discontinued:

- In asymptomatic patients with no clinical evidence of congestive heart failure:
 - If the absolute decline from baseline in EF is >10% AND the post-baseline EF is <50%; e.g., 60% →49%)

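### Protocol 4.6.1 requires all three drugs to stop for cardiac toxicity, while 7.5.2 requires only odalasvir (ODV) to stop for confirmed PR >300 msec or confirmed second degree or higher AV block

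*Protocol*

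**What the plan says.** Protocol 4.6.1 (Subject Treatment Discontinuation Criteria) names the three drugs and makes the stop permanent: "study drug treatment (AL-335, SMV and ODV) must be permanently discontinued if" any listed condition applies. One of those conditions reads "The subject has evidence of muscle injury (Section 7.5.1) or cardiac toxicity (Section 7.5.2 and 7.5.3", with no qualifier on which cardiac findings are meant.

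Protocol 7.5.2 (Cardiotoxicity) grades its action by event:

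- First degree block with PR above 240 and up to 300 msec, confirmed: "Based on this assessment, the study drugs may or may not be continued".
- PR above 300 msec, confirmed by a repeat triplicate at least 30 minutes after the "initial assessment, irrespective of presence or absence of clinical symptoms), ODV must be discontinued".
- "If a second degree or higher AV block is diagnosed", again confirmed by a repeat triplicate at least 30 minutes after the "initial assessment and irrespective of presence or absence of clinical symptoms), ODV must be discontinued".

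For the last two, the Investigator and Sponsor Medical Monitor "must determine whether or not continued dosing with AL-335 and SMV is acceptable for subjects that discontinue ODV". Only after these rules does 7.5.2 open a separate list under which all study medication stops, and that list concerns ejection fraction.

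**The concern.** Both sections are operative safety rules, and they prescribe different minimum actions for the same confirmed ECG finding. A reader who starts from 4.6.1 stops three drugs. A reader who starts from 7.5.2 stops one and opens a discussion about the other two.

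The event is not remote. Protocol 1.3 names the heart as a target organ of ODV toxicity, and 1.3.1 reports PR prolongation and first degree AV block in dogs. Protocol 1.2.1.2 mentions one case in this study of progressive PR prolongation with Wenckebach phenomenon, among 123 subjects dosed by 6 February 2017. Protocol 1.3.2 equates Wenckebach with type 1 second degree block, so a case of that type, if confirmed, falls where the two sections differ.

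At stake are consistent handling of the main ODV cardiac concern in a study whose primary endpoint is safety, and a clear basis for calling a given action compliant or a deviation. The choice also changes the regimen received. It can move the end of treatment as well, because SAP 3.2 closes the treatment phase 3 days after the latest last-intake date, and SVR12 is timed from actual end of treatment.

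**Working it through.** The plan gives no figure on this point and no arithmetic applies. The check sets the sections side by side, event by event.

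| Event | Protocol 4.6.1 | Protocol 7.5.2 or 7.5.3 | Result |
|---|---|---|---|
| First degree block, PR >200 to 240 msec | Not named separately | 7.5.2: drugs can continue | No mandatory stop in 7.5.2 |
| First degree block, PR >240 to 300 msec, confirmed | Not named separately | 7.5.2: discretionary | No mandatory stop in 7.5.2 |
| PR >300 msec, confirmed | All three stop | 7.5.2: ODV must stop; AL-335 and SMV by joint decision | Differ |
| Second degree or higher AV block, confirmed | All three stop | 7.5.2: ODV must stop; AL-335 and SMV by joint decision | Differ |
| Ejection-fraction criteria that stop all drugs | All three stop | 7.5.2: all stop | Agree |
| QTc >500 msec or change >60 msec, judged clinically significant | All three stop | 7.5.3: all stop | Agree |

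Next, for the two rows that differ, take each possible action:

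1. Stop all three drugs. This meets 4.6.1. It also meets 7.5.2, provided the joint decision on AL-335 and SMV has been made.
2. Stop ODV and continue the other two. 7.5.2 allows this. 4.6.1, read literally, does not.

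Only the second action exposes the conflict, but 7.5.2 expressly provides for it.

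Then, does another section settle it?

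- **Section 5.7.** When one drug is stopped, the Medical Monitor must be contacted about stopping the rest, unless the protocol already sets a specific requirement. Here it sets two, and they differ, so 5.7 gives no answer.
- **Section 4.7.1.** Mobitz type 2 or third degree block, if adjudicated to have at least a possible relation to the regimen, stops dosing in every subject. 4.6.1 lists a 4.7.1 trigger among its own conditions. For those blocks a third rule therefore applies and overrides the discretion in 7.5.2. Confirmed PR above 300 msec and type 1 second degree block are not named in 4.7.1. They come under it only if the event also counts as a serious, severe or life-threatening cardiac event. Higher-degree block adjudicated as unrelated is also left to 4.6.1 and 7.5.2.

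Finally, compare the other bullets of 4.6.1. Rash is limited to Grade 4, which matches Table 7-1, where Grade 3 stops SMV alone. Bilirubin is limited to confirmed Grade 4 that signals worsening liver disease or has no explanation, which matches Table 7-5. Both bullets are narrowed in words to the cases in which all drugs stop. The cardiac bullet is not.

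**The case against.** The strongest reply is that the cardiac bullet is only a pointer. It cannot mean every finding in the cited sections, since 7.5.1 continues treatment through many creatine kinase elevations and 7.5.2 does so for the shorter PR bands. Section 7.5.2 has its own list for stopping everything, and that list is the natural target of the pointer. The rash and bilirubin bullets show the same intent. On this reading 7.5.2 governs and nothing conflicts.

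This is coherent and may be what was meant, but 4.6.1 does not say it. The comparison with rash and bilirubin also cuts the other way: where the authors wanted only the all-drug cases, they wrote the limit into the bullet. A site has reason to take the cardiac bullet at face value.

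A second reply is that the decision in 7.5.2 is shared with the Sponsor Medical Monitor, so sites do not act alone, and that 4.7.1 removes related higher-degree block from the dispute. Both points stand and narrow the practical exposure. They do not make continuation of two drugs consistent with 4.6.1.

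A third reply is that the analysis already copes. SAP 6.5 lists administration dates for each drug, so subjects who continue without ODV can be identified. This stands, and no SAP change is needed.

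**Conclusion.** The inconsistency is real, in current text, and confined to two events: confirmed PR above 300 msec and confirmed second degree or higher AV block. The same event can be handled differently depending on the section followed. The conclusion assumes that 4.6.1 is read as written, with 7.5.2 cited whole.

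Three stronger readings are tempting but not supported:

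- **That the two sections cannot both be followed.** They can, by stopping all three drugs after the joint decision.
- **That any AV block is affected.** First degree block with PR up to 300 msec carries no mandatory ODV stop.
- **That one subject handled differently moves SVR12 or the discontinuation rate by 5 to 10 percentage points in a cohort of 20 or 10 (1/20 = 5%, 1/10 = 10%).** Under SAP 9.2.1, SVR12 rests on HCV RNA results alone, and Protocol 8.2 counts SVR whether or not the regimen was completed. A shift would need the subject's virologic outcome to change, which nothing in the documents shows. SAP 8.1 tabulates adverse events that led to stopping any of the study drugs, so an ODV stop is counted under either rule.

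Frequency can be gauged only from the single Wenckebach case among 123 dosed subjects (1/123, about 0.8%). The text available does not say how that case was managed.

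**What to change.** Reconcile Protocol 4.6.1, 4.7.1, 5.7 and 7.5.2. For confirmed PR above 300 msec, and for confirmed second degree or higher AV block, state the consequence for each of the three drugs once. Say how this relates to the study-level rule in 4.7.1 for Mobitz type 2 and third degree block, and have the cardiac bullet in 4.6.1 refer to that statement. The ejection-fraction criteria that stop all drugs and the QTc rule need no change on this point. The documents do not settle which rule was intended, and none is proposed here; that is for the sponsor and the investigator.

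The cost is a wording change in a protocol amendment. Marking subjects who continue without ODV in the SAP's administration listing is optional and adds little.
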